16.1.1 Data archive

Detailed procedures for data archiving at Vadu Rural Hospital and CMC Vellore are described in SOP VEL 2/1

After completion of the study, the Data Management Centre will keep copies of Databases, all CRFs and study related documents in a secure place for at least 5 years in compliance with GCP and regulatory requirement for investigational products.

16.1.2 Record keeping

See SOP VEL 2/1

After completion of the study, the investigators will keep his copies of all CRFs and source documents in a secure place for at least 5 years in compliance with GCP and regulatory requirements for investigational products.

17 Financing and insurance

This study will be supported by World health Organization - Initiative for Vaccine Research. In accordance with GCP guidelines, the Sponsor will provide an insurance policy for the conduct of the trial.

18 Publication policy

This study will be performed within the framework of a larger programme of research, consisting of several individual projects that relate to the development of safe and effective products against measles. In this connection, it has been deemed necessary for all rights to the results of the work to be performed under this project to vest exclusively in WHO. Consequently, General Conditions for publication will be as follows:

1. The Institution shall deliver to WHO at the end of the clinical trial the results of the work performed under this Agreement, unless otherwise agreed.

2. The Institution shall maintain in confidence all results of the work performed under this clinical trial, including information and tangible products of any kind whatsoever, unless authorized by WHO to disclose or publish such results. Notwithstanding the foregoing, the parties hereto recognize the public health benefits that may be achieved through the publication of the results of the project in accordance with normal academic practice.

Therefore, the parties agree that subject to the terms of this general condition 2, the Institution and the Principal Investigator may publish or present the results of this project. In the event of any intended publication or presentation as aforesaid, the Institution and Principal Investigator shall transmit to WHO for its review any material intended to be published or otherwise publicly disclosed, sixty (60) days before it is transmitted to any publisher, editor, referee or

meeting organizer. Within this sixty day review period, WHO may make a written request to the Institution and the Principal Investigator to remove from such material:

• any proprietary and confidential information disclosed by or on behalf of WHO to the Institution and the Principal Investigator hereunder, as well as

• any results generated hereunder, but only to the extent in order to achieve WHO public sector objectives- WHO reasonably deems it necessary to maintain such results in confidence in order to promote the development of such results into a useful health related product in collaboration with a commercial enterprise.

The Institution and the Principal Investigator agree to comply with any such request. Except to the extent WHO has made a request as aforesaid within the sixty day review period, the Institution and the Principal Investigator shall have the right to proceed with the publication or other public disclosure without further notice to WHO.

3. All rights to the results of the work to be performed under this project, including but not limited to copyright and the right to apply for, hold and exercise patent rights in respect of any invention resulting from the work, are vested exclusively in WHO. The Institution and Principal Investigator shall provide WHO with their full cooperation to permit the effective exercise of the above rights."

19 Organisational structure

Numbers of staff required (study field workers, nurses, doctors)

19.1.1 List of references to literature and data that are relevant to the trial, and that provide background for the trial

- 1. [name] AM, Strebel P, John Hoekstra E, Birmingham M, Bilous J. Experience in global measles control, 1990-2001. *J Infect Dis.* May 15 2003;187 Suppl 1:S15-21.
- 3. World Health Organisation, United Nations Children's Fund. WHO/UNICEF Global Immunization Vision and Strategy 2006–2015. WHO/IVB/05.05. http://www.who.int/vaccines-documents/DocsPDF05/GIVS_Final_EN.pdf.
- **4.** World Health Organisation. WHO Expert Committee on Biological Standardization : Forty-third report, Technical Report Series 840 1994.
- 5. [name], Kraemer S, Schneider M, Restrepo AM. Immunogenicity and safety of aerosolized measles vaccine: systematic review and meta-analysis. *Vaccine*. 2008;26(3):383-398.
- 6. Aerogen. OnQ: How does it work? http://www.aerogen.com/how-does-it-work.html, 2008.

Appendix 1: Diagram of Vaccine and Nebulizer Components

Appendix 2: Terms of Reference of the Independent Data Safety and Monitoring Board (DSMB). Updated, Nov 26, 2009 to "Data and Safety Monitoring Board Charter"

Appendix 3: Adverse Events, Descriptions and Definitions

Appendix 4: Forms for Protocol Changes

Appendix 5: Study Documents:

- SD-1 Investigator's Brochure
- SD-2 Study Synopsis
- SD-3 Study Timetable
- SD-4 Patient/Parent/Guardian Information Sheet
- SD-5 Informed Consent Forms for Parent/Legal Guardian
- SD-6 Sample CRFs

Appendix 6: Standard Operating Procedures (SOP) for the Study

Note: All SOPs are in draft format and will be finalized during training sessions before the start of the trial.

SOP No.	Title
Vadu Site	
VAD 1/1	Communication with Ethics Committee
VAD 2/1	Training Policy for Study Staff
VAD 3/1	Subject Identification and Recruitment Procedures
VAD 4/1	Informed Consent, Eligibility, Randomization and Vaccination (procedures
	on day of vaccination)
VAD 5/1	Procedures for Follow-up for Measles Aerosol Clinical Study (day 3 to 365
	Post Vaccination)
WHO	
WHO 1/1	Adverse Event Reporting and Management
WHO 2/1	Immediate Adverse Event Reporting and Management
WHO 3/1	Serious Adverse Event Reporting and Management
WHO 4/1	How to Transport, Store and Handle Measles Vaccine, Diluent, Syringes and
	Safety Boxes
WHO 5/1	Translation back/translation
WHO 6/1	Administration of the Measles Vaccine by the Subcutaneous Route
WHO 7/1	Procedures for Entering Data into CRFs on PDA
Vellore	
VEL 1/1	Statistical Analysis Plan
VEL 2/1	Data management plan (quality assurance and correct allocations
	administered)
VEL 3/1	Blinding laboratory to allocation
VEL 4/1	Randomization
Health Prot	tection Agency
HPA 1/1 🖊	Collection of Blood Specimen (Venous Blood) and Shipping to Vadu Shridi
	Saibaba Hospital (SSH)
HPA 2/1	Separation of Serum from Blood Samples at Vadu Laboratory and Transport
	to Testing Laboratory
HPA 3/1	Safe Disposal of Blood Sample Residues and Contaminated Waste
HPA 4/1	Aliquoting of Serum Samples and Storage in Freezers at Testing Laboratory
HPA 5/1	Detection of Anti-Measles Virus IgG by Enzyme Immuno Assay (ELISA)
	Using Enzygnost Dade Behring Kit and the BEP III ELISA Processor
HPA 6/1	Detection of Anti-Measles Virus IgG by Enzyme Immuno Assay (ELISA)
	Using Enzygnost Dade Behring: Manual Performance
HPA 7/1	Plaque Reduction Neutralization Test (PRNT) for Measles Antibodies
HPA 8/1	Checking the Calibration of Variable Volume Pipettes
Nektar/Aer	ogen
NEK 2/1	Preparation of Vaccine and Nebulizer and Administration by Aerosol Using
	Aerogen's Clinical Nebulizer to Infants from 9 – 12 Months.

Please note that several minor corrections have been made to the protocol, mostly typographical errors and a few discrepancies in descriptions different parts of the protocol. These are described below and are highlighted in the protocol.

- The Protocol number was assigned according to the numbering system decided for the Phase I clinical trials (Sponsor/project/country/number). This was WHO/MAP/IN/002. However, this was typed incorrectly on page 2 of the Protocol as WHO/MAP/IND/02. This has been corrected. This number is now in agreement with all other study documents (CRF, ICF, IND and all SOPs).
- Correction of the spelling of Principal: from Principle to Principal. Page 6, and page 45.
- 3) Section 4.3.5.4 page 17. Trial Setting Vadu Rural Area.

Statement that three additional health centres have been added to the area for recruitment has been added to page 17. The information in the Protocol had not been updated to give details of these areas but the information is available on request.

4) Minor revision to section 5.4.1 Immunogenicity page 21

To collect blood from a subsets of children at 28 days and one year after vaccination. The subsets will be randomly selected from all children enrolled in the Vadu study area because they will be able to be followed up within the infrastructure of an existing demographic and health surveillance system.

Subset is singular.

5) Section 6.3.1 Randomization. See SOP VEL 4/1 page 23

This procedure was separated from SOP VEL 1/1 "Statistical Analysis" as a separate SOP.

6) Section 6.3.1.2 Sequence generation page 23

"Stratified by area" has been removed, now reads: "The allocation sequence will be computer-generated random numbers, in permuted blocks, stratified by area, generated by an independent statistician."

7) Section 6.4.2.2 title corrected page 26

Title now "Method of packaging and labelling of the vaccine device.

8) Section 7.1 Inclusion criteria page 28

Revised point 3 to include subset of infants at Vadu.

Now reads: "Parent/guardian willing for child to be randomized and willing for child to be followed up for at least 91 days (364 days for Vadu subset)."

9) Section 8.2 and 8.3 page 29. Delete "plaque forming units" and replace with "CCID50".

The potency assay for the measles vaccine is measured in 50% Cell Culture Infectious Doses (CCID50) not in pfu. Change for accuracy of units.

10) Section 8.5.1.2 Visit 2 page 32.

Assignment of a unique Subject ID number is described in SOP VAD 4/1, not VEL 1/1.

11) Page 45. Delete highlighted phrase "atypical measles syndrome" mistakenly left on this page.

Phase II/III
Clinical Trial

STATISTICAL ANALYSIS PLAN

SOP No. VEL 1/1	Version-3
Written by: [name]	Replace Version: Nil
Edited by: -	Issue Date: September 11, 2012
Reviewed by: [name] and [name]	Effective Date:
Approved by: [name] and [name]	

Abbreviations

AE	: Adverse event
CDMC	: Clinical Data Management Centre
CFR	: Code of Federal Regulations (USA Food and Drug Administration)
CMC	: Christian Medical College (Vellore, India)
CRF	: Case Report Form
ELISA	: Enzyme-linked immuno-sorbent assay
GCP	: Good Clinical Practice
ICH	: International Conference on Harmonization
ID	: Identification number
MAP	: Measles Aerosol Project
MAR	: Missing at random
MySQL	: My Structure Query Language
PHC	: Primary Health Centre
PHP	: Personal Home Page
PRNT	: Plaque reduction neutralisation test
Promasys	: Protocol management system
SAS	: Statistical Analyses System
SAE	: Serious Adverse Event
SAP	: Statistical Analysis Plan
SOP	: Standard Operating Procedure
SSH	: Shirdi Saibaba Hospital
VCS	: Validation Check Specification
WHO	: World Health Organization
DSMB	: Data Safety Monitoring Board
OD	: Optical Density

Phase II/III	WHO Measles Aerosol Vaccine	Protocol
Clinical Trial	Project	WHO/MAP/IN/002

Table of Contents:

Section	Content	Page
1.	Study Title	3
2.	Background and Purpose	3
3.	Policy and Scope	3
4.	General Responsibilities	3
5.	Materials and Equipments	3
6.	Assessment of Outcomes	4
7.	Measures taken to Minimize Bias	5
8.	Sample Size	6
9.	Data Management and Pre-analysis Statistical Review	7
10.	Description of patient flow and Analysis dataset	8
11.	Statistical Methods	8
12.	Efficacy Analyses	25
13.	Safety Analyses	34
14.	Interim Analyses	43
15.	Trial Termination	48
16.	References	48
17.	Appendices:	49
	DSMB Report Format : Appendix 1	
18.	Additional Analyses	58

1.0 Study Title:

Pivotal study to evaluate the immunogenicity and safety of a measles vaccine given by aerosolized inhalation: randomized controlled trial.

2.0 Background and Purpose of this Document:

Background:

The pivotal study has been designed to evaluate an aerosolized formulation of measles vaccine as part of the Measles Aerosol Project (MAP). The current subcutaneous measles vaccine is known to be highly effective and safe and is recommended worldwide. The trial has therefore been designed to show that the immunogenicity of aerosolized measles vaccine is not inferior to the subcutaneous vaccine, and has an acceptable safety profile. The pre-determined maximum acceptable difference in the primary outcome between aerosolized and subcutaneous vaccines is 5%.

Purpose:

This document describes principles and procedures for statistical aspects of the randomized controlled trial protocol. The document is referred to as the Statistical Analysis Plan (SAP). The contents of the SAP are in accordance with the guidelines of the International Conference on Harmonisation (ICH) of Technical Requirements for Registration of Pharmaceuticals for Human Use and the Consolidated Reporting Standards for Trials extension to non-inferiority trials (1).

3.0 Policy and Scope:

The SAP is applicable to procedures for the statistical analysis of data generated during the MAP trial to be undertaken at Vadu, Maharashtra, India. The planned analyses are outlined in the protocol WHO/MAP/IND/002 August 2008, Section 11.

4.0 General Responsibilities:

The Principal Statistician is responsible for carrying out the statistical analysis of the clinical data according to the protocol and this SAP and to ensure that other responsible staff members perform their duties according to this SAP.

5.0 Materials and Equipments:

Hardware:

- 1. Desktop personal computers with MS Windows Network
- 2. Laptops with MS Windows Network

SOP VEL 1/1:	Statistical Analysis Plan	Page 3 of 61
September 11, 2012		

Software:

1.	Website development	:	XAMPP 1.6.6a (PHP 5.2.5, MySQL 5.0.51a, Apache), Apache friends group, Germany
2.	Statistical Analyses	:	SAS 9.1, SAS Institute Inc., Cary, NC, USA
3.	Audit trail software		Promasys 6.0, PROMASYS BV, Leiden, The Netherlands

6.0 Assessment of Outcomes:

The planned primary and secondary outcomes, and timing of their measurement, are outlined below.

6.11mmunogenicity:

6.1.1 Primary Outcome:

Measles seropositivity at day 91 post vaccination. This is defined as an optical density value (OD) >=0.1 or a plaque reduction neutralisation test (PRNT) result of >=120mIU/ml. Samples with an OD<0.1 at day 91 will be tested by PRNT as well as all samples from the Vadu study site.

6.1.2 Secondary Outcomes:

For all infants:

- Geometric mean ODs, pre-vaccination and at day 91;
- Seroconversion (defined as a change from Enzygnost enzyme-linked immunosorbent assay (ELISA) OD <0.1 to OD >=0.1 (unless PRNT results are available, in which case it is a change from PRNT from <120 to >= 120 mIU/ml) measured in paired samples from day 0 and day 91

For infants from Vadu in 28 and 364 days subsets:

- Geometric mean titres and ODs at days 0,28,91 and 364 and geometric mean fold changes between these time points to describe evolution of antibody response
- Seropositivity at 364 days in infants with antibody titre >=120 mIU/ml at day 91.
- Seropositivity at days 0, 28, 91 and 364 and changes between these time points

6.2 Safety:

6.2.1 Primary Outcome:

Adverse events (AE) up to and including day 91 post vaccination; AE include acute clinical reactogenicity, other AE, and serious or unexpected AE.

SOP VEL 1/1:	Statistical Analysis Plan	Page 4 of 61
September 11, 2012		

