6.2.1.2 Secondary outcomes

For all infants:

- Geometric mean titres, pre-vaccination and at day 91;
- Seroconversion (defined as a change from Enzygost OD <0.1 to OD ≥0.1 or PRNT from <120 to ≥120 mIU/mL) measured in paired samples from day 0 and day 91;

For infants from Vadu in 28 and 364 days subset:

- Geometric mean titres at days 28 and 364 to describe evolution of antibody response at days 0, 28, 91, 364;
- Seropositivity at 364 days in infants with antibody titre \geq 120 mIU/ml at day 91.

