8.6.3 Sample processing

8.6.3.1 Laboratory measurement of immunogenicity

- All serum samples will be tested by Enzygnost Anti-measles-virus/IgG ELISA (Dade-Behring, Marburg, Germany) (SOP HPA 5/1 and SOP HPA 6/1).
- In addition, all specimens with Enzygnost optical density readings <0.1 will be tested by plaque reduction neutralization test (SOP HPA 7/1).

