12.1. Efficacy Analyses: Immunogenicity

 Table 12.1.1A: Results of ELISA and PRNT, by study group, per-protocol analysis

	Baseline		Day	y 91
	AER	SC	AER	SC
	n=	n=	n=	n=
ELISA result (optical density)				
Median				
Interquartile range				
Min – Max				
Geometric mean titre				
95% CI	n=	n=	n=	n=
PRNT result (mIU/ml)				
Median				
Interquartile range				
Min – Max				
Geometric mean titre				
95% CI				

Legend:

AER – aerosol; SC - subcutaneous

For PRNT titre, includes subjects whose OD values are < 0.1 and all from Vadu site

SOP VEL 1/1:	Statistical Analysis Plan	Page 24 of 61
September 11, 2012		

	Baseline		Day 91	
	AER	SC	AER	SC
	n=	n=	n=	n=
ELISA result (optical density)				
Median				
Interquartile range				
Min – Max				
Geometric mean titre				
95% CI	n=	n=	n=	n=
PRNT result (mIU/ml)				
Median				
Interquartile range				
Min – Max				
Geometric mean titre				
95% CI				

Table 12.1.1B: Results of ELISA and PRNT, by study group, ITT analysis

Note: For PRN titre, the subjects whose OD values are < 0.1 and from Vadu site

12.1.2: Day 91 ELISA and PRNT results

Table 12.1.2A: Aerosol Group

	PRNT <120	PRNT >=120	PRNT not done	Total
Day 91 ELISA <0.1				
Day 91 ELISA >=0.1				
Day 91 ELISA Not done				
Total				

Legend:

Boxes highlighted in yellow represent results classified as seropositive at day 91

Phase II/III	WHO Measles Aerosol Vaccine	Protocol
Clinical Trial	Project	WHO/MAP/IN/002

Table 12.1.2B: Subcutaneous Group

	PRNT <120	PRNT >=120	PRNT not done	Total
Day 91 ELISA <0.1				
Day 91 ELISA >=0.1				
Day 91 ELISA Not done				
Total				

Legend:

Boxes highlighted in yellow represent results classified as seropositive at day 91

Table 12.1.3: Measles seropositive at day 91 post-vaccination (all infants) and difference in positivity between study arms

	AER n/N	AER%, 95% CI	SC n/N	SC%, 95% CI	Difference (AER- SC), 95% CI*
Seropositive at day 91					

Legend:

AER – aerosol; SC – subcutaneous;

* This difference is used to interpret non-inferiority, estimated by Wilson score method (5) (6).

Table 12.1.4A: Comparison of serological outcomes, by study group and time of sample collection: **Per Protocol cohort**

	AER		SC		Difference	
Time point	n	%	n	%	(AER-SC) 95% CI	
Day 0, seropositive						
Day 91, seropositive						
Day 91, seroconversion						

Legend:

AER – aerosol; SC - subcutaneous

Phase II/III	WHO Measles Aerosol Vaccine	Protocol
Clinical Trial	Project	WHO/MAP/IN/002

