Table 12.1.4B: Comparison of serological outcomes, by study group and time of sample collection: **ITT cohort**

	AER		SC		Difference	
Time point	n	%	n	%	(AER-SC) 95% CI	
Day 0, seropositive						
Day 91, seropositive						
Day 91, seroconversion						

Legend:

AER – aerosol; SC - subcutaneous

Table 12.1.5A: Comparison of serological outcomes, by study group and time of sample collection for Vadu subset: **Per Protocol cohort**

	AER		SC		Difference	
Time point	n	%	n	%	(AER-SC) 95% CI	
Day 0, seropositive						
Day 28, seropositive						
Day 28, seroconversion						

Legend:

AER – aerosol; SC - subcutaneous

Table 12.1.5B: Comparison of serological outcomes, by study group and time of sample collection for Vadu subset: **ITT cohort**

	AER		SC		Difference		
Time point	n	%	n	%	(AER-SC) 95% CI		
Day 0, seropositive							
Day 28, seropositive							
Day 28, seroconversion							

Legend:

AER – aerosol; SC - subcutaneous

Table 12.1.6A: Comparison of serological outcomes, by study group and time of sample collection for Vadu subset: **Per Protocol cohort**

Time point		AER		SC	Difference	
		%	ó n %		(AER-SC) 95% CI	
Day 0, seropositive						
Day 364, seropositive						
Day 364, seroconversion						

Legend:

AER - aerosol; SC - subcutaneous

SOP VEL 1/1:	Statistical Analysis Plan	Page 27 of 61
September 11, 2012		

Phase II/III	WHO Measles Aerosol Vaccine	Protocol
Clinical Trial	Project	WHO/MAP/IN/002

Table 12.1.6B: Comparison of serological outcomes, by study group and time ofsample collection for Vadu subset: **ITT cohort**

Time point		AER		SC	Difference	
		%	n	%	(AER-SC) 95% CI	
Day 0, seropositive						
Day 364, seropositive						
Day 364, seroconversion						

Legend:

AER – aerosol; SC - subcutaneous

Table 12.1.7: Day 0 and 91 ELISA and PRNT results with Sero-Conversion. (highlighted in yellow)

	Day 91									
				ELISA <().1]	ELISA >:	=0.1	ELISA Not done	
		PRNT	<120	>=120	Not done	<120	>=120	Not done	<120	>=120
	ELISA	<120								
	<0.1	>=120								
y 0)		Not done								
le (Da	ELISA	<120								
Baselin	>=0.1	>=120								
		Not done								
	ELISA	<120								
	Not done	>=120								
		Not done								

Note: Highlighted in grey are the ones, which are "Not Applicable". That is, which are seropositive or unknown at baseline

Phase II/III	WHO Measles Aerosol Vaccine	Protocol
Clinical Trial	Project	WHO/MAP/IN/002

		GMTs		
	AER	SC	Ratio AER/SC	95% CI for
				ratio
Day 0				
OD (all)				
Day 91				
OD (all)				
OD				
(OD >0.1)				
PRNT				

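### Secondary seroconversion is scored by a different assay depending on study site and day-91 OD, so some identical paired sera give different outcomes at Vadu and elsewhere

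*Supplement*

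**What the plan says.** Four statements govern this outcome.

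- **SAP 6.1.2** defines seroconversion as an ELISA change from OD <0.1 to >=0.1, "unless PRNT results are available, in which case it is a change from PRNT from <120 to >= 120 mIU/ml". It does not say whether a PRNT result must be available on both days or only one.
- **SAP 6.1.1** says which samples get PRNT: "Samples with an OD<0.1 at day 91 will be tested by PRNT as well as all samples from the Vadu study site". Day-0 sera outside Vadu are not mentioned.
- **Protocol 8.6.3.1** has a wider rule, with no condition on day or site: "all specimens with Enzygnost optical density readings <0.1 will be tested by plaque reduction neutralization test".
- **Protocol 6.2.1.2**, repeated in 9.2, has no override: "Seroconversion (defined as a change from Enzygost OD <0.1 to OD ≥0.1 or PRNT from <120 to ≥120 mIU/mL". A change on either assay is enough.

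The result shells add two details. Tables 12.1.1A and B have baseline and day-91 PRNT columns, and the legend to 12.1.1A reads "For PRNT titre, includes subjects whose OD values are < 0.1 and all from Vadu site". Table 12.1.7 crosses both assays on both days, with rows and columns for tests not done, and sets aside infants "which are seropositive or unknown at baseline". Tables 12.1.4A and B report day-0 seropositivity, but the SAP defines seropositivity only for day 91.

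**The concern.** A binary outcome should depend on the infant's sera, not on where the infant was enrolled. Here the PRNT override is fully in force only at Vadu. The eight areas in SAP Table 11.12.1 share one seroconversion estimate, so that estimate mixes two definitions.

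Site mix should balance between arms on average under 1:1 randomisation. Day-91 OD is different: it is measured after randomisation and is itself a response to the vaccine. Outside Vadu it decides whether a day-91 PRNT exists, so the share of infants scored by each assay can differ between aerosol and subcutaneous arms.

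The outcome matters because the entry criteria do not exclude infants who already carry antibody, and the primary outcome counts anyone positive at day 91. Seroconversion is the all-site outcome meant to set those infants aside. It is also the measure on which the systematic review in protocol 4.3.1.2 reports lower aerosol rates below 10 months of age.

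**Working it through.** **Plan's own figure.** No stated figure rests on the seroconversion rule. The sample size rests on day-91 seropositivity (90% in both arms, margin 5%, one-sided 2.5%, power 90%; SAP 8.1):

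n per arm = 2 × 0.9 × 0.1 × (1.960 + 1.282)² / 0.05² = 757. With continuity correction it is 797 per arm, or 1594 in total, and 1594/0.8 = 1993. This agrees with the stated 1600 and 2000, and nothing below changes it.

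**Enumeration.** Each infant has OD <0.1 or >=0.1 and PRNT <120 or >=120 on each of two days, giving 2⁴ = 16 patterns. Each was scored under SAP 6.1.2, first at Vadu (PRNT on both days) and then elsewhere under three readings of the testing rule.

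| Testing outside Vadu | Scored differently outright | Only one PRNT result | Scored differently if ELISA is used when the pair is incomplete |
|---|---|---|---|
| SAP 6.1.1 literally: day-91 OD<0.1 only | 4 | 8 | 6 |
| Protocol 8.6.3.1: every OD<0.1 specimen | 1 | 8 | 5 |
| Table 12.1.1A legend per infant: both sera if day-91 OD<0.1 | 4 | 0 | 4 |

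No reading brings the count to zero. The patterns that show why:

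| Pattern | Vadu | Elsewhere |
|---|---|---|
| A: OD <0.1 to >=0.1, PRNT <120 both days | Not a converter | Converter by ELISA when there is no PRNT pair |
| B: OD <0.1 to >=0.1, PRNT >=120 both days | Not a converter | Converter by ELISA when there is no PRNT pair |
| C: OD >=0.1 both days, PRNT <120 to >=120 | Converter | Not a converter |
| D: OD <0.1 both days, PRNT <120 to >=120 | Converter | No PRNT pair under literal SAP 6.1.1; converter under the other two readings |

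**Effect of the Table 12.1.7 note.** Suppose infants seropositive on either assay at day 0 are set aside. C then drops out everywhere. B drops out at Vadu, and elsewhere only if its day-0 serum had PRNT. A stays in, because it is negative on both assays at day 0. Under the protocol rule, A outside Vadu has a day-0 PRNT only: it is a converter if *available* means both days, and has no defined score if one day suffices. At Vadu it is a non-converter, although it is seropositive on the primary outcome. SAP Tables 12.1.2A and B provide a cell for this day-91 combination.

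**Illustration of size, on assumed inputs only.** Let a be the share with day-0 OD<0.1 but PRNT>=120 (5–20%), b the share with day-0 OD>=0.1 (2–5%), p the share with day-91 OD>=0.1 (85–90%), and q the share of the rest with PRNT>=120 (25–50%). Assume every OD>=0.1 serum has PRNT>=120 and that the two days are independent.

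- Rate scored by ELISA: (1−b)p. Rate scored by PRNT: (1−a−b)(p + (1−p)q).
- Lowest gap (a 5%, b 2%, p 85%, q 50%): 0.98 × 0.85 = 0.833 against 0.93 × 0.925 = 0.860, or −2.7 points.
- Highest gap (a 20%, b 5%, p 90%, q 25%): 0.95 × 0.90 = 0.855 against 0.75 × 0.925 = 0.694, or +16.1 points.
- OD<0.1 on both days, day-91 PRNT>=120 and no day-0 PRNT, under literal SAP 6.1.1: (1−b)(1−p)q, from 0.95 × 0.10 × 0.25 = 2.4% to 0.98 × 0.15 × 0.50 = 7.4% of infants outside Vadu.

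The gaps are between two ways of scoring the same sera, not between arms.

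**The case against.** The strongest reply is that the documents do not say day-0 sera outside Vadu go untested. The SAP 6.1.1 sentence stands under a day-91 outcome, protocol 8.6.3.1 covers every specimen, SAP 4.0 binds the statistician to both documents, and Table 12.1.1A has a baseline PRNT column. This stands. A reader might infer that weak responders outside Vadu cannot be scored, but that follows only from the literal SAP 6.1.1 reading; under the protocol rule pattern D has a PRNT pair. (Table 12.1.8 lists PRNT only at day 91, so the point is open either way.)

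A reader might also infer that day-0 serostatus depends on the day-91 result. That needs the per-infant reading of the Table 12.1.1A legend, under which no infant lacks a pair. The two inferences cannot both hold.

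Table 12.1.7 may classify the mixed cells by colour, which is lost in the text available. That could settle how a cell is read. It cannot remove the inconsistency, because the same sera fall into different cells by site.

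Finally, no decision rule uses seroconversion, laboratory staff are blinded, and pre-vaccination titre is also handled as a secondary objective and a covariate. All true. These limit the consequence but do not make the definition coherent.

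**Conclusion.** The point holds for the secondary seroconversion outcome and the day-0 serostatus tables. The SAP's override, its testing rule and the protocol's two statements cannot all be followed, and under each reading some identical sera are scored differently, or scored at Vadu and left without a defined score elsewhere. Pattern A shows this without depending on whether day-0 sera outside Vadu had PRNT.

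The size is not known. It depends on how often the two assays disagree, which the documents do not report. The ranges shown are illustrations, and neither they nor the share without a PRNT pair should be set against the 5% margin: that margin is a between-arm difference in a different outcome. A difference in scoring between arms is possible through day-91 OD, but its direction cannot be stated.

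The primary outcome uses one rule at every site ("This is defined as an optical density value (OD) >=0.1 or a plaque reduction neutralisation test (PRNT) result of >=120mIU/ml", with every day-91 OD<0.1 sample tested), so it, the margin and the sample size are unaffected.

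**What to change.** 1. In SAP 6.1.2, delete the clause that lets PRNT override ELISA when available.
2. Align SAP 6.1.1 with protocol 8.6.3.1: PRNT on every day-0 and day-91 specimen with OD<0.1, at all sites.
3. Define serostatus by the protocol 9.1 two-step rule on both days and at all sites: positive if OD>=0.1, or if OD<0.1 and PRNT>=120. Define seroconversion as negative at day 0 and positive at day 91. Each of the 16 patterns then has one result: 12 are positive at baseline, 3 convert and 1 stays negative.
4. Report PRNT-only seroconversion (<120 to >=120) as a separate Vadu outcome.
5. Relabel Tables 12.1.4A/B and 12.1.7 to match, and state the class of each not-done cell in words. Amend the definition in protocol 6.2.1.2 and 9.2 so that both documents agree.

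The cost is wording and table shells, plus day-0 PRNT testing that the protocol already specifies and for which 8.6.2.2 sets aside an aliquot.

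If day-0 PRNT was not done outside Vadu, use ELISA-only seroconversion at all sites and still report the Vadu PRNT outcome separately. This is consistent and needs no assays, but the SAP should state its limits: it keeps infants who are PRNT-positive and ELISA-negative at baseline, and it counts infants with day-91 OD<0.1 and PRNT>=120 as non-converters although they are successes on the primary outcome.
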